10.0 Statistical Considerations

10.1 Power analyses and sample size calculations. Previous studies have demonstrated a moderate effect (effect size ~0.4) of early palliative care on TOI, which is the primary outcome of the SCOPE trial. Assuming a type I error rate of 5% and a common standard deviation of 18.1 in the FACT-G TOI score in each group, 98 subjects in each group at 90 days (total N=196) would provide the study with at least 80% power to detect a change of 7.28 points (an effect size of 0.4) for TOI, the primary outcome of the SCOPE trial. Assuming 15% loss to follow-up at 90 days, enrolling 118 patients per group (total N=236) would provide this level of power. The study will not be powered to meet the secondary and exploratory outcomes.

The demographic and clinical characteristics of patients will be described using descriptive statistics. For continuous variables, median and interquartile range will be used while categorical variables will be described using frequency (percentage).

To examine the unadjusted effect of treatment on the primary end-point for the SCOPE trial, 90-day functional status as measured by the FACT-G TOI, we will use the Wilcoxon rank-sum test. In addition to unadjusted analyses, we will also perform multivariable regression to adjust for a priori-selected risk factors for outcomes, including age, frailty, cancer type, insurance status, education level, and degree of religious involvement. We will choose the type of multiple regression by carefully examining the distribution of the data. In the case of non-normally distributed outcomes, we will use a multivariable proportional odds regression model. To determine the unadjusted effect of early PCC on hospital length of stay, survival, and other time-to event outcomes, the cumulative incidence probability of these outcomes will be estimated via the Kaplan-Meier product limit method, and the log-rank test will be used to compare groups. Cox proportional hazards regression will be used to analyze the adjusted effect of PCC on time-to-event outcomes, with censoring as appropriate. To evaluate the unadjusted association between early PCC and receipt of intensive life-prolonging therapy in the last two weeks of life,

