chi-squared tests will be used. A logistic regression model will be used for adjusted analysis to estimate the odds of receiving intensive life-prolonging therapy due to early PCC. Missing data will be imputed using a model-based imputation process. Non-linear effects of continuous variables will be fit using restricted cubic splines, and modern regression model building techniques will be used. All covariates included in the adjusted models will be selected a priori and the model complexity will be based on the general rule that a model must fit no more than $m/10$ parameters to allow for proper multivariable analysis and to be generalizable to future patients, where m is the effective sample size. Graphical techniques will be used to perform model diagnostics and evaluate assumptions. Multicollinearity will be assessed using variance inflation factors and in the event of highly collinear variables, principal component analysis will be used.

10.2 Missing Data. When data cannot be collected, we will impute missing variables via multiple imputation methods. Missing data are common due to deaths and loss to follow-up. While our team has a proven track record of achieving high follow-up we will carefully analyze whether particular baseline demographics are associated with missing evaluations of long-term testing.

10.3 Statistical Meetings. The VCC will work regularly with our statisticians at the ongoing weekly biostatistics meetings. Final analyses will occur during the last 6 months of the study period, when monitoring, quality checks, data lock, archiving and manuscript preparation will take place.

11.0 Privacy/Confidentiality Issues. Protected Health Information (PHI) will be kept confidential and shared with other investigators or regulatory bodies only when in accordance with relevant governmental and institutional policies. At no time will we reveal subject identities in any manner, whether in presentation, description or publication of the research for scientific purposes. All data obtained with subject or provider identifiers will be kept in locked file cabinets to ensure confidentiality, and all paper file contents will be shredded before disposal. All subjects will be assigned a unique study number for use in the computer database, and all electronic data will be kept in password-protected computer files to ensure confidentiality.

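### The adjusted model for 90-day TOI is left to be chosen from the trial data, without a criterion, an arm-masked look or a fixed effect measure

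*Combined protocol and SAP*

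**What the plan says.** Section 4.2.1 defines the primary endpoint as the 90-day FACT-G TOI score with adjustment for the baseline score; Aim 1 in section 1.0 says the same.

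Section 10.1 gives two analyses of it. The unadjusted one is fixed: a Wilcoxon rank-sum test. The second is a multivariable regression on six risk factors (age and frailty, type of cancer, insurance, education and religious involvement). Baseline TOI is not named among them. On the form of that regression the plan says: "We will choose the type of multiple regression by carefully examining the distribution of the data". The next sentence is a partial rule: "In the case of non-normally distributed outcomes, we will use a multivariable proportional odds regression model". Later in the section, after specifying restricted cubic splines, it adds that "modern regression model building techniques will be used", and then that covariates are set a priori within a limit on the number of parameters.

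The design target is on the points scale. The evaluable sample "would provide the study with at least 80% power to detect a change of 7.28 points (an effect size of 0.4) for TOI".

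Masking is described for the outcome assessors (sections 6.2 and 7.2.2). None is described for the analyst, and section 6.1 has the trial's primary biostatistician create the randomization scheme. Section 10.3 places data lock and final analyses in the last six months of the study but sets no point at which the model is decided.

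**The concern.** The plan does not say:

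- what test or cut-off makes an outcome non-normal;
- whether raw scores or residuals are examined;
- whether the look is pooled or by arm, or when it takes place;
- which model applies if the data look normal (linear regression is the natural reading, but it is not named);
- whether the Wilcoxon test or the regression is the primary analysis.

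The gap matters because of the endpoint definition. A Wilcoxon test on 90-day scores does not adjust for baseline. Only the regression can, and the regression is what remains undecided.

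Two things are at stake. First, the effect measure: a linear model would report a difference in points, comparable with the 7.28-point target, while proportional odds reports an odds ratio. A reader cannot tell in advance which will appear. Second, error control: if the result is near the threshold and the choice rests on judgement, the conclusion can depend on that judgement.

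**Working it through.** **The plan's own figure.** Inputs from section 10.1: "a common standard deviation of 18.1 in the FACT-G TOI score in each group", a difference of 7.28 points, 5% type I error (two-sided assumed) and 80% power.

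- n per arm = 2(1.960 + 0.842)² × 18.1² / 7.28² = 2 × 7.849 × 6.18 = 97.04, rounded up to 98. This matches the plan. A one-sided test would need 77, which does not match.
- Power at 98 per arm: √(98/2) × 7.28/18.1 − 1.960 = 2.815 − 1.960 = 0.855, and Φ(0.855) = 0.804.
- After 15% loss: 98/0.85 = 115.3, so 116 per arm against 118 stated; 118 × 0.85 = 100.3 evaluable. The difference is immaterial.

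The sample size therefore reproduces, and it rests on a comparison of means in points.

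**Effect of the open choice on type I error.** No closed form applies, so this was simulated under no treatment effect: 98 per arm, one baseline covariate with correlation 0.5, 8,000 trials per setting. The models were linear regression and proportional odds (outcome grouped into 12 levels), both adjusted for the covariate, plus the unadjusted Wilcoxon test. The error distributions, the correlation and the grouping are assumptions, not figures from the documents. Monte Carlo standard error: √(0.05 × 0.95/8000) = 0.24 points at 5%, and about 0.3 points at 9%.

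| Strategy (nominal 5%) | Normal | Mild left skew | Clear left skew |
|---|---|---|---|
| Linear, fixed | 4.95% | 5.09% | 4.93% |
| Proportional odds, fixed | 5.30% | 5.91% | 5.65% |
| Wilcoxon, fixed | 4.91% | 5.14% | 5.26% |
| Shapiro-Wilk on residuals, then linear or proportional odds | 5.03% | 5.96% | 5.65% |
| Smaller p of the two adjusted models | 6.40% | 7.24% | 7.37% |
| Smallest p of the two models and Wilcoxon | 8.34% | 9.32% | 9.60% |

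- The mechanical rule tracks the model it selects. It chose proportional odds in 4.9%, 94.6% and 100% of trials across the three settings and adds essentially nothing to that model's own rate.
- Picking the smaller p-value of the two adjusted models adds 6.40 − 5.30 = 1.10, 7.24 − 5.91 = 1.33 and 7.37 − 5.65 = 1.72 points over proportional odds fixed in advance.
- Letting the Wilcoxon test compete adds about a further 2 points (8.34 − 6.40 = 1.94; 9.32 − 7.24 = 2.08; 9.60 − 7.37 = 2.23). This is the cost of not naming a primary analysis.

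**Power cost of fixing the ordinal model when TOI is exactly normal.** Using the Wilcoxon efficiency of 0.955 as a guide, 98 × 0.955 = 93.6 effective patients per arm, and power falls from 80.4% to 78.6%. An unadjusted simulation at a standardized difference of 0.4 gave 79.4% for the t-test and 77.2% for Wilcoxon. Both are stand-ins for the adjusted models; they suggest a loss of about 2-3 points.

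**The case against.** The best defence has four parts.

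- **The choice is directed.** The plan names proportional odds for non-normal outcomes. A statistician who examines pooled scores, sees skew and uses that model has followed the plan, and the simulation shows little or no inflation from doing so. This stands, and it limits the concern to the missing criterion and safeguard.
- **The named test is not open.** The Wilcoxon test is fixed, and the regression is described as additional. This stands as far as it goes. But the Wilcoxon test does not deliver the baseline-adjusted endpoint, and the plan does not say which analysis is primary.
- **Covariates are fixed.** A reader might take the model-building clause to mean data-driven covariate selection. The documents do not support that: covariates are set a priori, the number of parameters is capped, and splines are specified. The discretion concerns mainly the type of model.
- **Nothing says that arm results are seen first.** A reader might infer that the analyst picks the model after seeing the treatment comparison. The text requires only that outcome data exist. A pooled look is compatible with it; a look by arm is permitted but not stated.

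A reader might also infer that the Wilcoxon test cannot be combined with the multiple imputation in section 10.2. That is a separate question and too strong: the documents do not say that the test is run on imputed data, and the Mann-Whitney probability is an estimate with a variance, so it can be pooled.

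**Conclusion.** The plan leaves the adjusted model for 90-day TOI, and with it the effect measure, to be settled from the trial data. There is no criterion, no arm-masked look and no named model for the normal case. This affects the only planned analysis that can match the endpoint as defined.

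The numerical risk is modest. Type I error is 5.0-6.0% under a mechanical normality rule, about 6-7% if the more favourable of two adjusted models is chosen, and about 8-10% if the Wilcoxon test is also a candidate. The last two are upper bounds under deliberate selection. They are not estimates of what the plan produces when followed in good faith, and nothing in the documents suggests that such selection is intended. They also depend on the assumed correlation of 0.5, the assumed error shapes, the 12-level grouping, and linear regression being the unnamed alternative. The uncertainty about the effect measure depends only on that last assumption.

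**What to change.** Replace the sentence on choosing the type of regression with one adjusted model, fixed before treatment codes are merged with outcomes. For example:

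- Analyse 90-day TOI with the proportional odds model the plan already names, whatever the distribution of TOI.
- Include baseline TOI and the a priori covariates, with spline knots fixed in advance, and replace the general clause on model building with that specification.
- Name this as the primary analysis and keep the Wilcoxon test as supportive.
- Report the odds ratio and the model-based difference in mean TOI, each with a 95% CI, so that the result can be set against the 7.28-point target.
- Check the proportional odds assumption and say how the check will be reported. The model does not need normality, but its common odds ratio rests on this assumption.

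The cost is wording. The sample size stays at 98 evaluable and 118 enrolled per arm. If TOI is exactly normal, about 2-3 points of power are lost relative to a linear model with the same covariates. Adjusting for baseline works the other way: at an assumed correlation of 0.5 it removes 0.5² = 25% of the outcome variance.

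Fixing linear regression with baseline TOI in advance would also cure the defect and would report directly in points. If the sponsor prefers a data-driven choice, the plan should state the criterion, name both models, and require a pooled, arm-masked look before unblinding.

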1.0 Introduction

Cancer represents a significant burden of aging. When comparing those over 65 years to those under 65, the incidence of cancer is 10 times greater, and the cancer death rate is 16 times greater.¹ Care for older adults with surgically-treated gastrointestinal (GI) or genitourinary (GU) malignancies imposes particular burdens because the treatments are highly morbid, especially in older adults with multimorbidity. For instance, pancreatic cancer is the fourth leading cause of cancer deaths with 70% of this mortality occurring in patients over 65, and nearly three-quarters of patients die within 5 years of resection.^{1,2} Surgeons face a quandary: resection is the only chance for cure, but resection potentially increases suffering.

Concurrent palliative care consultation (PCC) with oncologic care improves clinical outcomes earlier in the illness trajectory as well as at the end of life (EOL).³ PCC reduces use of intensive life-prolonging therapy at EOL while improving quality of life (QOL) and other patient-centered outcomes.^{4,5} Early PCC concurrent with chemotherapy improves survival for patients with advanced malignancies.^{4,6} **PCC also has been associated with improved surgical outcomes,⁷ yet surgeons frequently call for such expertise only as a last resort. There is a dearth of literature to help surgeons understand how PCC can benefit surgical patients with serious age-related conditions, such as abdominal malignancies.**

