4.2.3 Exploratory Endpoints

- [1] FACT-G TOI score [180 days, trend over study period]
- [2] FACT-G score [180 days, trend over study period]
- [3] PROMIS Anxiety-6 score [90 days, 180 days]
- [4] PROMIS Depression-6 score [90 days, 180 days]
- [5] Satisfaction with hospital stay [30 days]
- [6] Time from surgery to adjuvant therapy
- [7] Overall Survival [3 years]
- [8] Post-traumatic Growth Inventory score [180 days]
- [9] Karnofsky Performance Status [90 days, 180 days, trend over study period]
- [10] Employment [trend over study period]
- [11] Number of hospital admissions over study period
- [12] Number of ER visits over study period
- [13] Long-term care residence [trend over study period]
- [14] Life Space Assessment Questionnaire score [trend over study period]
- [15] Zarit Burden Interview [90 days, 180 days, trend over study period]

4.2.4 Planned Subgroup Analysis: Patients who die during the course of the study will be included in a subgroup analysis with the following outcomes.

- [1] Receipt of chemotherapy within 14 days of death
- [2] Hospice enrollment of less than 7 days before death
- [3] Days at home without ER visit or hospital stay in last 30 days of life
- [4] Location of death (home vs. facility)
- [5] Quality of end-of-life care (FATE-S score)

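### Kaplan-Meier is named for the cumulative incidence of outcomes that death can preclude, so probabilities of discharge alive and of starting adjuvant therapy will be overstated if deaths are censored

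*Combined protocol and SAP*

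**What the plan says.** Section 10.1 sets one method for a group of outcomes, described as the "unadjusted effect of early PCC on hospital length of stay, survival, and other time-to event outcomes". For all of them "the cumulative incidence probability of these outcomes will be estimated via the Kaplan-Meier product limit method". For the unadjusted comparison of arms, the plan states that "the log-rank test will be used to compare groups". Adjusted analyses use Cox regression, "with censoring as appropriate".

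The outcomes that fall under this sentence are:

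- **Overall survival.** Secondary at 1 year (section 4.2.2), exploratory at 3 years (section 4.2.3).
- **"Time from surgery to adjuvant therapy".** Exploratory (section 4.2.3).
- **Hospital length of stay.** Named in section 10.1 and collected in the data timeline of section 7.2, but not listed as an endpoint in section 4.2.

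No section mentions competing risks. No section says whether a patient who dies in hospital, or before adjuvant therapy, is censored, counted as an event or kept in the risk set. Section 10.2 refers to deaths only as a source of missing data: "Missing data are common due to deaths and loss to follow-up".

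**The concern.** The quantity that section 10.1 names, a cumulative incidence, is the proportion of all patients who have had the event by a given time. When deaths are censored, Kaplan-Meier estimates something else: the proportion who would have had the event if nobody died first. Censored patients are assumed to have the same future chance of the event as those still at risk. For someone who has died, that chance is zero.

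For overall survival the question does not arise, because death is the event. For discharge alive and for the start of adjuvant therapy it does. What is at stake is the accuracy of the published percentages, such as the proportion in each arm who had started adjuvant therapy by 90 days. Aim 2 hypothesises that the intervention lengthens life, so the size of the error could also differ between arms.

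**Working it through.** **The plan's own figures.** The documents state no rate or precision for length of stay or any time-to-event outcome, so there is nothing to reproduce on this point. The only sample-size calculation is for the primary endpoint. With SD 18.1, difference 7.28 and two-sided 5% alpha, 2 × (1.960 + 0.842)² × (18.1/7.28)² = 97.04, rounded up to the stated 98 per group. It does not depend on the estimator discussed here.

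**Inputs.** The estimator and its scope come from section 10.1. All event and death rates below are assumptions. The one mortality figure in the documents is background for pancreatic cancer (section 1.0): "nearly three-quarters of patients die within 5 years of resection".

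**Model for time to adjuvant therapy.** Take constant cause-specific hazards *a* (start of therapy) and *d* (death), with the time point scaled to 1.

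- Mortality by the time point: m = 1 − exp(−d)
- True cumulative incidence: C = a/(a+d) × [1 − exp(−(a+d))]
- 1 minus Kaplan-Meier with deaths censored: K = 1 − exp(−a)
- Excess: K − C

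Worked case, C = 60% and m = 10%: d = −ln(0.90) = 0.1054. Solving for *a* gives 0.9857. Check: 0.9857/1.0911 × (1 − exp(−1.0911)) = 0.9034 × 0.6642 = 0.600. Then K = 1 − exp(−0.9857) = 0.627, an excess of 2.7 points.

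Excess in percentage points:

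| Mortality by the time point | True initiation 40% | 60% | 70% |
|---|---|---|---|
| 2% | 0.4 | 0.5 | 0.6 |
| 5% | 0.9 | 1.3 | 1.4 |
| 10% | 1.9 | 2.7 | 2.9 |
| 15% | 3.0 | 4.1 | 4.5 |

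The range is therefore 0.4-2.9 points for 2-10% mortality and 0.9-4.5 points for 5-15%. Here m is mortality by the time point, whether or not therapy had started. The share dying before starting therapy is smaller, about 1.2-7.8% across the 2-10% rows.

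If the share dying before therapy (*b*) is fixed instead, the total hazard is −ln(1 − C − b) and *a* is the fraction C/(C+b) of it. With C = 60% and b = 10%: 1.2040 × 0.6/0.7 = 1.0320, so K = 64.4%, an excess of 4.4 points. Over C = 40-70%, the excess is 0.2-0.5 points for b = 1%, 1.2-2.6 for 5% and 2.6-5.5 for 10%.

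**Anchor.** 75% dead at 5 years under a constant hazard is −ln(0.25)/5 = 0.277 per year. That implies 6.6% dead at 90 days and 12.8% at 180 days. With C = 40-70%, the excess is 1.3-1.9 and 2.5-3.8 points. This covers only one of the eligible cancers.

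**Length of stay, if the event is discharge alive and deaths are censored.** This was checked by simulating 1,000,000 stays (log-normal, median 7 days to discharge alive and 10 days to in-hospital death, log-scale SDs 0.6 and 0.8; all assumed).

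| In-hospital mortality | Excess at day 14 | Excess at day 30 |
|---|---|---|
| 1% | 0.4 | 0.8 |
| 3% | 1.3 | 2.4 |
| 5% | 2.1 | 4.0 |

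If the stay ends at discharge or death, every stay ends in an event and the excess is zero. For overall survival it is also zero.

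**Difference between arms.** Suppose true initiation is 60% in both arms and mortality is 12% in one and 6% in the other. The hazards *a* are 1.001 and 0.956, so K is 63.3% and 61.6%, a gap of 1.7 points where the true proportions are equal. With 118 per arm, the standard error of a difference in proportions is √(2 × 0.6 × 0.4/118) = 6.4 points. The gap is about a quarter of that.

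**The case against.** **The bias depends on a choice the plan does not state.** A reader might infer that the published probabilities are bound to be too high. The documents do not establish this. They define neither the length-of-stay event nor the handling of death, and two possible conventions give no excess: ending the stay at discharge or death, or keeping the dead in the risk set. This stands, and the point is conditional for that reason. But censoring deaths is the usual practice with Kaplan-Meier, and nothing in the plan directs otherwise.

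**Adjuvant therapy may be analysed among survivors.** Section 7.2.2 lists its initiation among outcomes evaluated in survivors at about 90 days, in patients for whom an oncologist judges it would be recommended. On that reading, no death competes in a simple 90-day proportion. Adjuvant therapy is also absent from that section's 180-day list, so the higher mortality range corresponds to no stated 180-day analysis. Both observations are fair, but neither settles the separate time-from-surgery endpoint in section 4.2.3, which falls under the Kaplan-Meier sentence.

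**The tests are not wrong.** A reader might infer that log-rank and Cox must be replaced, or that a false treatment effect will appear. The documents do not support either. With deaths censored, both methods validly compare cause-specific hazards. In the 12% versus 6% example the initiation hazards really do differ (1.001/0.956 = 1.047), so the Kaplan-Meier contrast reflects that difference and misleads only as an absolute probability. Gray's test answers another question. With *a* = 0.956 in both arms and the same two mortality rates, the cumulative incidences are 58.4% and 60.0%, a difference caused by mortality alone. Choosing it is a choice of estimand.

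**The outcomes are minor.** One is exploratory, the other is not listed in section 4.2, and section 10.1 says the trial is not powered for secondary or exploratory outcomes. This limits the importance of the point but does not make the estimator correct.

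**Conclusion.** The point holds in conditional form. Section 10.1 names a cumulative incidence and assigns it an estimator that does not deliver one when death precludes the event and is censored. No other section closes the gap.

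The direction is certain under that handling, because the excess is positive whenever anyone dies before the event. The size is modest and rests wholly on assumed rates and constant hazards: roughly 0.4-2.9 points for adjuvant initiation at 2-10% mortality by the time point, and 0.9-4.5 points at 5-15%. Any distortion of an arm difference is small against sampling error.

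This is a matter of accurate reporting for minor outcomes and does not threaten the trial's main conclusion. The cost of correcting it is low enough that it should be done.

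**What to change.** In section 10.1:

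1. Keep Kaplan-Meier, log-rank and Cox for overall survival.
2. Define the event for hospital length of stay. If it is discharge alive, treat in-hospital death as a competing event. If it is discharge or death, say so; Kaplan-Meier may then stay.
3. For discharge alive and time from surgery to adjuvant therapy, estimate cumulative incidence by the Aalen-Johansen method with death as a competing event.
4. Keep log-rank and Cox for these outcomes, state that deaths are censored there, and label the results as cause-specific. Gray's test may be added if a comparison of cumulative incidences is wanted, but it is optional.
5. State whether time to adjuvant therapy is analysed in all patients judged suitable or only in 90-day survivors, so that sections 4.2.3, 7.2.2 and 10.1 agree.

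The cost is a few sentences and a standard software call. Dates of death are already in the data timeline of section 7.2, so no new data are needed. The only downside is that the reported probabilities will be slightly lower.
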